(2) To develop, using a mixed methods approach, a targeted educational intervention about prostate cancer for men who live in high risk neighborhoods

No hypothesis is being tested for this aim.

(3) To test the impact of the targeted intervention on levels of knowledge, anxiety, and informed decision making about PCa screening

Hypothesis 3a: Men in the prostate-specific intervention group will have higher levels of knowledge about PCa screening than those who receive the healthy lifestyle control intervention

Hypothesis 3b: Men who express a greater number of barriers to PCa screening will have higher levels of anxiety about PCa and PCa screening

Hypothesis 3c: Men in the prostate-specific intervention group will have higher levels of informed decision making about PCa screening than those who receive the healthy lifestyle control intervention

Sub-aim: To examine if there are differences in outcomes by intervention setting

(4) To observe the rates of PCa screening in the intervention and control groups

B. RESEARCH STRATEGY

B.1. Experimental Design

The proposed design is a mixed-methods study including quantitative analyses of state registry data, survey data and Philadelphia health statistics, qualitative analyses of focus group results, and the test of a targeted intervention to improve key factors associated with shared decision making and potential uptake of prostate cancer screening in high-risk neighborhoods. Table 2 provides a brief summary of the study populations, study outcomes, traits to be measured, and analytical methods proposed to accomplish each specific aim.

Table 2: Summary of Specific Aims and Study Methods

	Aim 1: Identify high risk neighborhoods	Aim 2: Develop intervention via mixed-methods approach	Aim 3: Test intervention in high risk neighborhoods
Sample Population	Estimates from 1995-2005 data: ~4,500 African-Amer. cases ~4,000 European Amer. Cases		200 At-Risk Men
Primary Outcomes	Prostate cancer mortality; tumor stage and grade		Prostate cancer knowledge, anxiety, intention to screen, PSA screening
Neighborhood Data	Demographics, PCa screening, other health behaviors, health conditions, SES		
Patient-Level Data	Race, age, marital status	Focus Group Results	

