It is anticipated that the small-group educational sessions will occur at sites that frequently draw middle-aged and senior men from the target population in each pre-selected neighborhood. This will include churches, barbershops, recreational centers, community development corporations, employment centers, and neighborhood restaurants. [54] MEE will identify and engage these types of establishments in each target neighborhood by drawing upon its vast network of community partners in Philadelphia. MEE will also conduct phone book and Internet searches to identify potential recruiting locations and sites for educational sessions. They will introduce the study to the leadership of each location and explain the requirements of holding a study intervention session at their facility. MEE will create informational packets for interested study sites to aide in the discussion. The only requirement of a study site is to provide a space for which the research team can conduct a study session. Recruitment for the study session will be done by the study team, although a site is welcome and encouraged to invite eligible men who it has contact with. Sites may agree to hold more than one session, provided that the study team leadership feels that an adequate number of participants can be recruited at that site. Study sites will be compensated based on the number of study sessions that occur on their premises.

B.4. Aim 3: To test the impact of the targeted intervention on levels of knowledge, anxiety, and informed decision making about PCa screening

B.4.a. Participant Recruitment

MEE will develop an e-mail blast, flyers for study site partners and recruiting information to recruit eligible men from the neighborhoods for participation. If these efforts need to be augmented, MEE will also conduct canvassing of key transportation corridors in the selected Philadelphia neighborhoods, to recruit potential study participants. The study team will also draw upon the community contacts and resources of the Penn Center for Community Health Workers to identify men eligible for participation. The goal is to enroll 200 men in the study over a period of 18 months. We anticipate, based on our previous experience in community-based research, that we will have to screen about 10 times that number, or about 2000 men, to reach our study recruitment goals.

B.4.b. Study Eligibility

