Study Intervention: Men who live in the Intervention Group Neighborhoods: After obtaining informed consent and administering the baseline survey, the health educator will show the short introductory video on a tablet computer. Then, the educator will use the curriculum booklet, one given to each participant, to review general information about the prostate gland, prostate incidence and development, risk factors, screening options, screening guidelines and the importance of repeat screening.[20] The educational session is meant to be interactive, with men feeling comfortable to ask questions and engage in a discussion with the educator and the other men at the session. Men Who Live in the Control Group Neighborhoods: After obtaining informed consent and administering the baseline survey, the health educator will show the short introductory video on a tablet computer. Then, the educator will use the curriculum booklet, one given to each participant, to review topics about health promotion actions related to diet, exercise, tobacco, general cancer screening and cardiovascular risk. The educational session is meant to be interactive, with men feeling comfortable to ask questions and engage in a discussion with the educator and the other men at the session. It is anticipated that the educational sessions for both groups will last about 15 minutes.

Post-Survey(s): Immediately following the intervention, men will complete a brief paper-and-pencil endpoint survey. The majority of items on the baseline survey, except for the demographic and contact information, will be repeated on the endpoint survey. Additionally, the study research assistant will call each enrolled participant at 1 month and 4 months after their enrollment date to administer the same endpoint survey. Participants who are not reached by telephone will be contacted by mail and by email to attempt to retain the maximum number of participants over time.

Participant Compensation: Participants will be compensated \$25.00 after completing the endpoint survey on the day of the intervention and \$25.00 for the completion of each follow-up survey.

Referral to Screening

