Men from both groups who decide that they want to be screened for prostate cancer will be linked with medical care at Thomas Jefferson University Hospital (TJUH) if the participant does not have a primary care physician for medical care. Participants will be encouraged to contact their primary care physician for screening, or in the absence of a primary care physician, [name] at TJUH, a study co-investigator and oncologist who specializes in high-risk populations, will provide screening at TJUH. In addition, [name] will care for any male who completes screening and requires follow-up medical care based on his test results. A letter of support

from [name] attesting her commitment to provide thorough medical care for any male who screens for prostate cancer as a result of this project is included in the application.

B.4.d. Analysis Plan

Since Aim 3 will not be addressed by a randomized trial design and we anticipate clustering of observations from the same neighborhood, linear and generalized linear mixed models having random intercepts corresponding to neighborhood will be applied to test the quantitative hypotheses. This approach will allow us to account for the correlation between participants from the same neighborhood and adjust the parameters of interest for potential confounding variables. Potential confounders will be identified and choices about specific models will be made after computing descriptive statistics to compare the distributions and identify imbalances of study variables between the groups (i.e., intervention vs. control) or variables (e.g., the number of barriers to screening) of interest for the given hypothesis. If substantial clustering also exists at the site level, this hierarchical correlation will also be incorporated into the models.

A sub-aim of this study will be to determine whether there are differences in results based on where the intervention is implemented. As neighborhoods often attract certain demographics of the population, so do various gathering places for men. Some gathering places may prove to be better for achieving the goals of this study – increasing PCa knowledge and shared decision making about PC a screening among high risk men. During aim 2, the content will be optimized for each setting and suggestions will be made for future interventions in these settings.

B.4.e. Power Analysis

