The target sample size is $n=200$ men. Since we anticipate 20% attrition, we will recruit and consent 240 evenly distributed across each of the 4 neighborhoods. In a local population similar to our target population, a previous prostate cancer screening decision making study [21] found that, compared to standard intervention controls, their decision support enhanced intervention lead to a 0.8 point increase ($SD = 1.5$) in knowledge on a 10-point scale. Assuming this in our target population, a type I error rate of 0.05, an intra-neighborhood correlation of 0.005 to 0.01, and that 4 to 10 neighborhoods will be sampled per group, the planned study should have approximately 80% to 94% power to detect this difference. In a similar prostate cancer screening shared decision making article [22], investigators found that their intervention lead to a 22% reduction ($SD = 0.15$) in prostate screening. Making similar assumptions as for the knowledge endpoint, we may be somewhat underpowered for detecting this difference in screening rates as the expected power would be approximately 50% to 67%. However, the primary goal is to increase knowledge about screening so that each man will make an informed decision taking into account his risk factors and personal preferences.

B.4.f. Results Dissemination

The study results will be disseminated to the neighborhood at the end of the project by multiple methods. Town hall meetings will be held in the targeted neighborhoods to explain the goals of the study and to provide a summary of results and additional PCa education to the community at-large. Next steps will be discussed, as well as ways to improve, sustain and expand targeted educational interventions around the Philadelphia region. Project newsletters and brochures will be made available to be shared with family and community members. The video developed during aim 2 for educational purposes will be shared at the town halls and will be made available on the internet for public education.

C. Potential Problems and Alternative Approaches

C.1. Geocoding

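### Men without a 1- or 4-month survey would add nothing to comparisons at those surveys, although their same-day scores are held; if loss differs by condition, these contrasts can be modestly biased

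*Combined protocol and SAP*

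**What the plan says.** - **Sample size (B.4.e).** "The target sample size is $n=200$ men", and then "Since we anticipate 20% attrition, we will recruit and consent 240", split equally over the four neighborhoods. B.4.a gives a different goal: "The goal is to enroll 200 men in the study over a period of 18 months". When the 20% is lost is not stated.
- **Surveys (B.4.c).** Men complete a baseline questionnaire before the session. "Immediately following the intervention, men will complete a brief paper-and-pencil endpoint survey". The same survey is given by telephone at 1 and 4 months, with mail and email as back-up and a payment for each survey.
- **Model (B.4.d).** "linear and generalized linear mixed models having random intercepts corresponding to neighborhood will be applied to test the quantitative hypotheses". A site level is added if clustering there is substantial. Confounders and specific models are chosen after the groups have been described.
- **Screening (Aim 4, A.1).** "To observe the rates of PCa screening in the intervention and control groups". How screening is ascertained is not stated.
- **What is absent.** For Aim 3 there is no analysis set, no missing-data method, no comparison of lost with retained men and no sensitivity analysis. H3a and H3c carry no time point. The only stated exclusion for missing data concerns registry cases without a census tract (C.1, Aim 1).

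**The concern.** Consent, baseline survey, session and same-day survey take place in one visit, so the natural reading is that most of the 20% is lost afterwards. By then each man has supplied two scores that predict his later ones.

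The stated model does not use that information. Fitted to the 4-month survey alone, it drops men who lack that survey. Fitted to all surveys stacked, a neighborhood intercept still treats a man's own surveys as unrelated apart from the weak correlation shared by his whole neighborhood (0.005 to 0.01 in B.4.e). His same-day score therefore does not inform his missing later score.

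The later contrast then compares men who could be reached. It is safe if loss is unrelated to score, or related in the same way in both groups. Condition is assigned by neighborhood without randomization and the two groups are taught different content, so equal selection cannot be taken for granted. At stake is a 1- or 4-month difference in knowledge or decision outcomes that is partly created, or partly hidden, by who was reached. Recruiting more men does not change that.

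**Working it through.** **1. The plan's headcount.** 200 × 1.20 = 240 reproduces the plan's figure. With 20% loss, 240 × 0.80 = 192 men remain and 48 are lost, about 24 per group. To keep 200 would need 200 / 0.80 = 250. This shortfall is a separate, small matter. The point here is what happens to the 48.

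**2. Bias by hand.** Let d be the share lost in a group and g the retained-men mean minus the lost-men mean. The bias in the retained-men difference is d_I × g_I − d_C × g_C. The SD of 1.5 is from B.4.e ("lead to a 0.8 point increase ($SD = 1.5$) in knowledge on a 10-point scale"); the gaps g are assumptions.
- Same loss and same gap in both groups: 0.20 × 0.75 − 0.20 × 0.75 = 0.
- Lost men 0.5 SD (0.75 points) lower in one group only: 0.20 × 0.75 = 0.15.
- Lost men 1 SD (1.5 points) lower in one group only: 0.20 × 1.5 = 0.30.

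**3. Simulation.** Inputs: SD 1.5, 120 men per group and 20% lost per group, from B.4.e. Assumptions: no true effect, equal correlation of 0.4, 0.6 or 0.7 among baseline, same-day and 4-month scores, logistic loss on the same-day score, and no neighborhood clustering, so that this issue is isolated. There were 4,000 runs per case. Entries are the bias in points at 4 months, over the three correlations.

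| Loss pattern | Odds of loss per SD | Retained men, raw | Retained men, baseline-adjusted | All men's baseline and same-day scores used |
|---|---|---|---|---|
| Low scorers lost in intervention, random in control | ×2 | 0.08 to 0.14 | 0.04 to 0.05 | 0.01 or less |
| Same | ×4 | 0.13 to 0.22 | 0.07 to 0.08 | 0.01 or less |
| Opposite directions in the two groups | ×2 | 0.15 to 0.27 | 0.09 to 0.10 | 0.01 or less |
| Opposite directions | ×4 | 0.26 to 0.46 | 0.15 to 0.17 | 0.01 or less |
| Same pattern in both groups | ×2 or ×4 | about 0 | about 0 | about 0 |

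The last row of opposite-direction loss is an extreme case, shown for completeness and left out of the range quoted in the conclusion. As shares of the planned effect, 0.04 / 0.8 = 5% and 0.098 / 0.8 = 12% with baseline adjustment; unadjusted, 0.08 / 0.8 = 10% and 0.27 / 0.8 = 34%. For one-sided loss, the nominal 5% test rejects in about 7% to 19% of runs unadjusted and 6% to 7% with baseline adjustment.

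**4. Screening.** Assume a true rate of 30% in both groups, with 15% and 25% of men unreached.
- If no unreached man was screened, reached-men rates are 0.30 / 0.85 = 35.3% and 0.30 / 0.75 = 40.0%, a false gap of 4.7 points.
- If unreached men screen at the same 30%, reached-men rates are correct. Counting the unreached as unscreened then gives 0.30 × 0.85 = 25.5% and 0.30 × 0.75 = 22.5%, a false gap of 3 points.
- With 20% unreached per group, the full-sample difference is 0.8 × (observed difference) + 0.2 × (difference among unreached men). It can therefore lie up to 20 points either side of 0.8 times the observed difference.

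**The case against.** The strongest reply is that silence is being read as a decision, and that the bias is conjectural.

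- **No text excludes lost men.** This is right. Exclusion is inferred from the model described, and B.4.d leaves specific models open. But no participant effect, within-man correlation or survey term is named, so omission is what the described model would do by default.
- **H3a and H3c have no time point.** This is also right. Tested on the same-day survey, they are hardly touched by later loss. A reader might infer that attrition biases both hypotheses; the documents do not support that. Only the 1- and 4-month comparisons are exposed.
- **Baseline adjustment removes much of the bias.** It does, and B.4.d permits it, though the baseline score is not named. The table shows one-sided bias falling to 0.04 to 0.08. A residual remains because the same-day score is still unused.
- **Nothing shows that selection differs by condition.** Call schedule, back-up contact and payment are the same in both groups, and the control session also covers general cancer screening. So differential loss is possible, not established.
- **The false-positive rates are not the plan's.** They ignore clustering, with two neighborhoods per condition. With an intra-neighborhood correlation of 0.01 and a test on the four neighborhood means, one-sided loss gave about 5% to 9%.
- **Screening.** A reader might infer that loss inflates both screening rates. That holds only if unreached men screen less. Ascertainment is not stated, Aim 4 carries no hypothesis, and same-day scores cannot stand in for later uptake.

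**Conclusion.** The concern holds in a limited form. The plan expects 20% attrition and gives no way for a lost man's baseline and same-day scores to inform the 1- and 4-month comparisons. If loss depends on the same-day score differently by condition, the later knowledge contrast can be off by about 0.08 to 0.27 points unadjusted and 0.04 to 0.10 with baseline adjustment. Decision scores are exposed in the same way, but the documents give no figures from which to size that.

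These sizes rest on the assumed correlation and loss patterns, and on an SD taken from a 10-point scale, whereas B.4.c describes a 17-item measure; the shares of 0.8 carry over better than the points. Selective loss is a risk that the design leaves open, not a demonstrated bias. The change is still worth making because it uses data already planned and removes nearly all of the bias when loss depends on observed scores.

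**What to change.** In B.4.d:

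1. Name the survey at which H3a and H3c are tested.
2. For the 1- and 4-month comparisons, define the analysis set as all consented men with a baseline survey. Fit one likelihood-based repeated-measures mixed model with same-day, 1-month and 4-month scores as outcomes, a within-man correlation (man nested in neighborhood), baseline score, and condition-by-survey terms.
3. Tabulate loss by condition and by same-day score.
4. For screening, state how it is ascertained and report the reached-men rate as the main figure. Give bounds for unreached men, including the case with all counted as unscreened, as a sensitivity analysis only, since that denominator can itself create a gap.

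The cost is analysis-plan wording and a little more programming, with no new data or visits. The later contrasts will then rest openly on a missing-at-random assumption.

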Descriptive analyses will be conducted to characterize high risk PCa census tracts compared to lower risk census tracts. Mapping the high risk census tracts will help us to determine how they are distributed within and around pre-defined Philadelphia neighborhoods (commonly used community names for each section of the city, Figure 2.) Those Philadelphia neighborhoods will become the target

neighborhoods for aims 2 and 3. Continuous variables will be analyzed with t-tests (or nonparametric alternative tests for variables without normal distributions) and categorical variables will be analyzed with frequency tables and chi square tests or Fisher's exact tests if any expected cell frequencies are small. Patient-level and neighborhood variables will be summarized for comparisons between high risk and lower risk neighborhoods to highlight factors that may be central topics of focus groups and intervention development. Correlations will be computed to examine the relationship between percent of cases with advanced disease and prostate-specific mortality rates. Regression modeling will allow us to determine significant trends in PCa incidence and mortality over time with and without adjustment for covariates such as the prevalence of risk factors including older age at diagnosis, African American residents and low neighborhood SES. We will also use the EpiQMS tool provided on the PA Department of Health website to determine age-specific incidence and mortality rates for Philadelphia. Generating maps of these data along with maps showing highest prevalence of PCa screening (CHDB data) will indicate where should target our focus groups and interventions for aims 2 and 3.

B2.f. Designation of Neighborhoods for Study Condition

Based on the GIS mapping results, the four neighborhoods in Philadelphia with the highest rates of late-stage PCa will be chosen to serve as study sites. Study condition (intervention or control) will be designated at the neighborhood level. Therefore, two of the sites will be designated as intervention neighborhoods and two will be designated as control neighborhoods. All men who live in the same neighborhood will receive the same intervention. All efforts will be made to ensure that the designations are done in a way that Intervention and Control neighborhoods are not geographically adjacent to each other, to avoid contamination of study messages among participants.

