Inclusion Criteria: Men ages 40-69 who currently reside in one of the four selected high risk neighborhoods will be eligible to participate in the study. This age range was selected based upon current screening recommendations for high-risk men. Additionally, the literature suggests that, when asked what age group might be most in need of prostate health information, men in this age group were frequently identified because they may not understand that they are susceptible to prostate cancer. [16, 17]

Exclusion Criteria: Men who do not reside in one of the four neighborhoods, who self-report that they have previously been diagnosed with prostate cancer, or who have had prostate cancer screening (PSA or DRE) within the past 12 months will be excluded from participating in the study.

B.4.c. Study Intervention

Because the level of designation for study condition will be at the neighborhood level, all men who reside in the same neighborhood will be in the same condition (intervention or control). Community health educators will go to participating study sites within the selected neighborhoods in pairs and will complete the following steps:

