As with many research studies, and particularly with community-based research studies, often participant recruitment and retention is difficult. In this study, the research team members have substantial experience in recruiting community-based samples, particularly in low-income/low-resource neighborhoods. [name] works closely with the Center for Community Engagement at the University of Pennsylvania, and [name] collaborates with the Center for Urban Health at Thomas Jefferson University; both of these centers have strong inroads into the neighborhoods of interest for this study. Additionally, MEE Productions has a network of community based partners in Philadelphia that will be useful in recruiting study sites and participants. The Center for Community Health Workers is extremely involved in local and grass-roots in Philadelphia and we can utilize their partner and organizational connections for recruitment. In terms of retention, participants will be compensated \$25 for each follow-up survey that they complete. We will maintain a database of contact information for each participant and will attempt to contact each participant via multiple methods to increase our retention rate. Lastly, our PCa survivors, who are study consultants, will offer suggestions for alternative recruitment and retention strategies.

REFERENCES

1. **SEER Cancer Statistics Review, 1975-2011**
[http://seer.cancer.gov/csr/1975_2011/](http://seer.cancer.gov/csr/1975_2011/)

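### Enrollment is balanced by neighborhood but not by calendar time, so the plan leaves room for time to be confounded with condition over the 18 months

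*Combined protocol and SAP*

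**What the plan says.** **Numbers and period.** B.4.e states that 240 men will be consented, "evenly distributed across each of the 4 neighborhoods", with an analysis target of 200. B.4.a gives the time frame: "The goal is to enroll 200 men in the study over a period of 18 months". No section gives a calendar by neighborhood or by condition.

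**Assignment.** Under B2.f, "two of the sites will be designated as intervention neighborhoods and two will be designated as control neighborhoods". B.4.d confirms that Aim 3 is not randomized. The one separation rule is spatial: efforts will be made so that "Intervention and Control neighborhoods are not geographically adjacent to each other". There is no corresponding rule for time.

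**Delivery and possible changes.** B.4.c says "Community health educators will go to participating study sites within the selected neighborhoods in pairs". B.3.d expects six educators, so about three pairs for four neighborhoods. B.4.a holds canvassing in reserve in case the first recruitment methods fall short. C.3 says that survivor consultants "will offer suggestions for alternative recruitment and retention strategies".

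**Measurement and model.** In B.4.c, knowledge is measured on the day of the session, before and immediately after it, and again 1 and 4 months after each man's own enrollment date. B.4.d specifies mixed models with a neighborhood random intercept and selects confounders after looking at imbalances. Enrollment date and baseline score are neither named nor ruled out. Hypotheses 3a and 3c compare levels between groups.

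**The concern.** Equal numbers per neighborhood do not make the two conditions contemporaneous. Each neighborhood can fill its 60 places at its own pace, in any part of the 18 months, without departing from the plan. Because condition is a property of the neighborhood and there are only two per group, a difference in when the two pairs of neighborhoods are worked is also a difference between conditions.

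Suppose that canvassing starts late and brings in men with different prior knowledge, or that an outside event changes what men know about screening. If one condition was mostly enrolled before the change and the other mostly after it, the change is added to or subtracted from the contrasts for Hypotheses 3a and 3c and the comparison of screening rates. Where enrollment periods overlap, a calendar term can help. Where they do not, time and condition are the same variable and no analysis can separate them. The safeguard therefore has to be in the scheduling, before enrollment starts.

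**Working it through.** **1. The plan's own figure.** Inputs from B.4.e: 200 men (100 per group), difference 0.8, SD 1.5, alpha 0.05 (taken as two-sided), intra-neighborhood correlation (ICC) 0.005 to 0.01, and 4 to 10 neighborhoods per group (k).

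- Effective n per group = 100 / [1 + (100/k − 1) × ICC]; power from a noncentral t with 2(k − 1) df.
- k = 4, ICC 0.01: 100/1.24 = 80.6, df 6, power 80.4%.
- k = 10, ICC 0.005: 100/1.045 = 95.7, df 18, power 93.7%.

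This matches the stated 80% to 94%. The point disputes no stated number, and concurrent enrollment leaves the sample size and this range as they are. (The power statement's 4 to 10 neighborhoods per group does not match the two in B2.f; that is a separate matter.)

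**2. Enrollment rate.** 240/4 = 60 men per neighborhood. 18 months = 6 quarters. 60/6 = 10 men per neighborhood per quarter, or 20 per condition.

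**3. Bias from drift.** If the mean knowledge score moves by d points per quarter in all neighborhoods alike, and mean enrollment dates of the two conditions differ by g quarters, then bias = d × g. The documents give neither d nor g. I assume d = 0.05 to 0.10 and vary g. The sign depends on the direction of drift and on which condition comes first. Points are on the 10-point scale of the cited study; the trial's own scale has 17 items, so the share of the planned 0.8 is the more useful figure.

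To bound g, take the four neighborhoods worked strictly one after another, 4.5 months each, with midpoints at 2.25, 6.75, 11.25 and 15.75 months (I = intervention, C = control):

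| Order | Mean dates (months) | Gap | Bias | Share of 0.8 |
|---|---|---|---|---|
| IICC or CCII | 4.5 and 13.5 | 9 months, 3 quarters | 0.15 to 0.30 | 19% to 38% |
| ICIC or CICI | 6.75 and 11.25 | 4.5 months, 1.5 quarters | 0.075 to 0.15 | 9% to 19% |
| ICCI or CIIC | 9 and 9 | 0 | 0 | 0 |

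Concurrent enrollment also gives a gap of zero.

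**4. Effect on the test.** Take a drift of 0.4 points over 18 months (0.4/6 = 0.067 per quarter, inside the assumed range), the 9-month gap, no true effect, two neighborhoods per group and ICC 0.01.

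- Bias = 0.067 × 3 = 0.20 points, or 25% of 0.8.
- Effective n = 100/(1 + 49 × 0.01) = 67.1 per group; standard error = 1.5 × √(2/67.1) = 0.259.
- The two-sided false-positive rate rises from 5% to 7.7% (t with 2 df) or 12.1% (normal test).

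**The case against.** The strongest reply is that the plan does not describe non-concurrent work at all. A reader might infer that sites, and hence conditions, will be taken in sequence; no section says so. A reader might also infer that the plan expects steady change over the period. The text supports little of that. B.3.d has all educators trained before the study starts and requires prior experience. C.3 promises only suggestions from consultants. The one concrete change is canvassing, which is contingent and is described for the selected neighborhoods without distinction by condition. Growing educator skill does not fit the drift model in any case: control sessions cover general health, so better delivery there has little route to prostate knowledge, while better delivery in intervention neighborhoods mainly alters the size of a real effect. These replies stand, and the point does not rest on educators.

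It would also be too strong to say that nothing measured on the man can help. Recruitment mix and earlier outside events shift the same-day baseline as well as the first post-session score, so baseline adjustment could remove that drift there. It would not cover events between the session and the 1- and 4-month surveys. Observed screening has no direct baseline counterpart, since B.4.b excludes men screened in the previous 12 months. The adjustment is also not pre-specified.

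B.4.d could admit enrollment date as a confounder, and the date will be known because follow-up is timed from it. That works only where periods overlap.

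Finally, recruitment is expected to be hard (about 2,000 men screened for 200 enrolled), so a rule closing a neighborhood that runs ahead would let the slowest one limit the study. This also stands, and the fix avoids such a rule.

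**Conclusion.** The concern holds as a conditional one. The plan permits intervention and control neighborhoods to be worked at different times and contains nothing, in design or named model terms, that prevents it. This is an omission, not a contradiction.

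The size is unknown. Under the assumed common drift of 0.05 to 0.10 points per quarter, the bias runs from zero to 0.15–0.30 points. A reader might take 19% to 38% of the planned difference as the expected bias. It is the worst case: fully separate halves, with no baseline adjustment. Of the six strictly sequential orders, only two produce it and two produce none; overlap would shrink the gap further.

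Concurrent enrollment would not make the comparison unconfounded. With two designated neighborhoods per condition, fixed differences between neighborhoods stay mixed with condition. The time component is nevertheless worth removing: it is under the study team's control, cheap to prevent, and beyond repair afterwards if the periods do not overlap.

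**What to change.** - **B.4.a and B.4.c:** state that intervention and control neighborhoods will be enrolled concurrently, with roughly equal numbers per condition per quarter (about 20, or 10 per neighborhood) as a scheduling target and not a hard stop.
- **B.4.a and C.3:** state that any recruitment or retention method added during the study, canvassing included, will start in all four neighborhoods at the same time.
- **B.4.d:** pre-specify enrollment period and baseline score as covariates in the Aim 3 models.

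The cost is scheduling effort, including moving about three educator pairs among four neighborhoods within each quarter, two sets of model terms, and possible short waits in a faster neighborhood. No extra men or staff are needed.
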